5.2.3 Prior and Concomitant Therapy

Any medication or vaccine (including over-the-counter or prescription medicines, vitamins and/or herbal supplements) that the subject is receiving from the time of signing consent, or received during the study, through the Treatment Period and 30 days after study drugs are stopped, must be recorded along with the reason for use, date(s) of administration including start and end dates, and dosage information including dose, route

and frequency. The investigator should review all concomitant medications for any potential drug-drug interactions.

During the Post-Treatment Period, all medications taken will be recorded until 30 days following the last dose of study drugs. After 30 days post-treatment, during the Post-Treatment Period, only antiviral therapies related to the treatment of HCV and medications prescribed in association with a serious adverse event (SAE) will be recorded in EDC.

[figure not shown]
The Primary Therapeutic Area Medical Director should be contacted if there are any questions regarding prior or concomitant therapy(ies).

5.2.3.1 Prior HCV Therapy

Subjects must be HCV treatment-naïve or treatment-experienced, with the exception of HCV GT3 treatment-experienced subjects who will not be eligible. Subjects will be considered treatment-experienced, if they have previously received HCV treatment with IFN or pegIFN with or without RBV or sofosbuvir with RBV with or without pegIFN. Receipt of any other investigational or commercially available direct acting anti-HCV agents other than sofosbuvir is not allowed.

Subjects will be categorized as:

- Treatment-naïve: subject has never received any treatment for HCV infection.
- Subjects with **an allowed prior treatment** will be categorized as:
 - Non-responder: HCV RNA detected at the end of a prior treatment course (except for breakthrough, which is captured separately). These subjects are further categorized as:
 - Null responder: failed to achieve a 1 log₁₀ IU/mL reduction in HCV RNA by Week 4 or a 2 log₁₀ IU/mL reduction in HCV RNA by Week 12 during a prior treatment course;

- Partial responder: achieved at least a 2 log₁₀ IU/mL reduction in HCV RNA by Week 12 during a prior treatment course but failed to achieve HCV RNA undetectable at the end of treatment;
- Unknown or unable to specify: insufficient data to categorize as null or partial responder.
- Breakthrough: confirmed ≥ 1 log₁₀ IU/mL increase from nadir or achieved HCV RNA undetectable (or unquantifiable) during a prior treatment course but HCV RNA was quantifiable during or at the end of treatment.
- **Relapse:** achieved HCV RNA undetectable at the end of a prior treatment course but HCV RNA was detectable following cessation of therapy.
- Other: subject received a prior treatment course and reason for not achieving SVR is other than above.
- Unknown: subject received a prior treatment course and reason for not achieving SVR is unknown.

[figure not shown]
Subjects must have completed or discontinued prior therapy at least 2 months prior to the Screening Visit in order to be eligible for the study.

5.2.3.2 Management of Immunosuppressant Agent Dosing

Drug-drug interaction studies have been conducted for ABT-493/ABT-530 co-administered with cyclosporine or tacrolimus and are detailed, along with the dosing recommendations during the Treatment Period as follows:

Dosing recommendations for tacrolimus management during treatment with ABT-493 and ABT-530 in this study are:

- For subjects who are initiating therapy with tacrolimus, the initial dose should be selected from the lower end of the recommended range as per the tacrolimus label (e.g., 0.10 mg/kg/day for adult liver transplant recipients).
- For subjects already taking tacrolimus, dosing should continue with close monitoring of tacrolimus trough levels and tacrolimus dose adjustment as needed.

Dosing recommendations for cyclosporine management during treatment with ABT-493 and ABT-530 in this study are:

[figure not shown]
• The dose of cyclosporine with ABT-493/ABT-530 (300/120 mg QD) should not exceed 100 mg once daily for entry into the study. If the cyclosporine maintenance dose needs to be increased to a total daily dose greater than 100 mg during the Treatment Period, discussion with the Therapeutic Area Medical Director should occur. Dosages of cyclosporine > 400 mg are not allowed during the Treatment Period.

For mTOR inhibitors, as the metabolic profile for both sirolimus and everolimus are similar to tacrolimus, management of sirolimus and everolimus will be similar to tacrolimus (refer to Section 3.0 for additional information).

- For subjects who are initiating therapy with sirolimus or everolimus, the initial
 dose should be selected from the lower end of the recommended range as per
 the sirolimus and everolimus labels.
- For subjects already taking sirolimus or everolimus, dosing should continue with close monitoring of drug trough levels and dose adjustment as needed.

During this study, the dosing of tacrolimus, cyclosporine, sirolimus and everolimus will be informed by scheduled blood level testing. Tacrolimus, cyclosporine, sirolimus and everolimus blood level testing may be performed at any time during the study at the investigator's discretion. Where possible, it is recommended that CNI and mTOR medications be taken with study drugs in the morning with food. Based on in vitro drug-drug interaction studies, no potential interaction is expected with azathioprine, MMF and mycophenolic acid. Subjects may be on azathioprine, MMF, and/or mycophenolic acid as per the investigator's discretion. Monitoring of azathioprine, MMF, and/or mycophenolic acid levels beyond what is standard and clinically indicated is not required.

CNI dosing in the study is guided by the recommended dose reductions based on healthy volunteer data and modeled to achieve trough levels appropriate in the post-transplant setting. Clinical experience suggests some differences may be observed between patients

EudraCT 2015-005616-14

in relation to cyclosporine or tacrolimus dosing and associated trough levels. Therefore CNI and mTOR dosing will be guided by frequent trough level estimates, particularly during the first weeks of treatment administration, and by the investigators clinical experience in the management of CNI and mTOR medications in liver or renal transplant recipients.

On Day 1 of the Post-Treatment Period, it is recommended that the pre-study dose of immunosuppressants tacrolimus, sirolimus, everolimus and cyclosporine be resumed. Further modifications in tacrolimus, sirolimus, everolimus and cyclosporine dosing or dose frequency should be guided by measuring trough levels.

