1.1 Protocol Amendment: Summary of Changes

Previous Protocol Versions

[figure not shown]
Protocol	Date	
Original	28 January 2016	
Amendment 1	26 May 2016	

The purpose of this amendment is to:

 Update Section 3.0, Introduction, and Section 5.2.3.2, Management of Immunosuppressant Agent Dosing.

Rationale: The protocol has been updated to provide clarification regarding cyclosporine dose adjustment during the Treatment Period for subjects requiring maintenance titration as per usual transplant standard of care. The dosing recommendation of 100 mg total daily dose is based upon the Phase 1 drug-drug interaction studies (Studies M13-584, M13-605) that examined cyclosporine doses of 100 mg and 400 mg, as described within the protocol. Stable dosing at or below cyclosporine 100 mg/day was selected as the entry criteria (Inclusion Criterion 14), as this dose demonstrated only mild increases in ABT-493 exposure when coadministered with ABT-493 and ABT-530. Although larger increases in ABT-493 exposure were observed with the cyclosporine 400 mg dose, all study drugs were well tolerated in both studies and no safety signals were identified. Coadministration with ABT-493 and ABT-530 did not affect exposure of cyclosporine at either dose level.

While the recommended dose of cyclosporine at the time of entry into the study (Inclusion Criterion 14) remains the same, clarification is needed for a subject who has entered into the study at a daily cyclosporine dose of 100 mg or less and requires an increase in the maintenance cyclosporine dose during the period of ABT-493/ABT-530 administration to > 100 mg/day. Cyclosporine doses > 400 mg have not been formally evaluated in DDI studies with ABT-493 and ABT-530, and cyclosporine doses should not exceed 400 mg/day when coadministered with ABT-493/ABT-530 under any circumstances. Contact with the Therapeutic Area MD should be made for any case requiring titration of the cyclosporine maintenance dose to greater than 100 mg to

discuss proper management of concurrent therapies in order to prevent unnecessary discontinuation of study drug and risk of resistance development due to incomplete therapy.

• Update Section 5.2.2, Exclusion Criteria, Criterion 7.

Rationale: Clarification that concurrent liver disease other than HCV as an exclusionary criteria is applicable in the post-transplant period.

• Update Section 5.1.2, Treatment Period, and Section 5.3.1.1, Study Procedures.

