Tacrolimus Phase 1 Data (Study M13-592): The effect of the combination of 300 mg ABT-493 and 120 mg ABT-530 at steady-state on the pharmacokinetics of a single dose of 1 mg tacrolimus and vice-versa was evaluated in healthy subjects. A single dose of 1 mg tacrolimus did not affect the steady-state exposures of 300 mg ABT-493 and 120 mg ABT-530. Tacrolimus exposures increased by 50% when co-administered with ABT-493 and ABT-530. All study drugs were well-tolerated and no safety concerns were identified. Based on these results, the following dosing recommendations for tacrolimus management during treatment with ABT-493 and ABT-530 are recommended in this study:

- For subjects who are initiating therapy with tacrolimus, the initial dose should be selected from the lower end of the recommended range as per the tacrolimus label (e.g., 0.10 mg/kg/day for adult liver transplant recipients).
- For subjects already taking tacrolimus, dosing should continue with close monitoring of tacrolimus trough levels and tacrolimus dose adjustment as needed.

Cyclosporine Phase 1 Data (Studies M13-584 and M13-605): Study M13-584 evaluated the effect of co-administration of single-dose and multiple-doses of 300 mg ABT-493 and 120 mg ABT-530 with a single dose of 100 mg cyclosporine. Pharmacokinetic results showed that a single dose of cyclosporine modestly increased the steady-state exposures of ABT-493 by 30% - 34% and of ABT-530 by 11% - 26%. The exposures of cyclosporine following a single dose of 100 mg were minimally affected by co-administration of single or steady-state doses of ABT-493 and ABT-530 (\leq 14% increase). All study drugs were well-tolerated and no safety concerns were identified.

[figure not shown]
Study M13-605 evaluated the interaction between a single dose of 300 mg ABT-493 and 120 mg ABT-530 and a single dose of 400 mg cyclosporine in healthy subjects. Preliminary pharmacokinetic results from this study showed that cyclosporine exposures were not affected by co-administration with ABT-493 and ABT-530. However, the exposures of ABT-493 increased 4.5 to 5.1-fold, and for ABT-530 increased 22% to 88% following co-administration of a single dose of 400 mg cyclosporine. All study drugs were well-tolerated and no safety concerns were identified.

Based on pharmacokinetic results from these two studies, the following recommendations are made for cyclosporine management during treatment with ABT-493 and ABT-530:

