 - O Subjects with indeterminate FibroScan[®] score ($12.5 \le \text{score} < 14.6$), must have a qualifying liver biopsy; or
 - A screening FibroTest score of ≤ 0.48 and Aspartate Aminotransferase to Platelet Ratio Index (APRI) ≤ 1 .

○ Subjects with indeterminate FibroTest (0.48 < result < 0.75), or conflicting FibroTest and APRI results (e.g., FibroTest \leq 0.48, but APRI \geq 1) must have a qualifying liver FibroScan[®] or biopsy.

Liver biopsy results will supersede Fibrotest[®]/APRI or FibroScan[®] results and be considered definitive. FibroScan[®] results will supersede Fibrotest[®]/APRI results for the determination of absence of cirrhosis.

- 10. Subjects must voluntarily sign and date an informed consent form, approved by an Institutional Review Board (IRB)/Independent Ethics Committee (IEC) prior to the initiation of any screening or study-specific procedures.
- 11. Subjects must be able to understand and adhere to the study visit schedule and all other protocol requirements.
- 12. Subject is a recipient of a cadaveric or living donor liver transplant which was a consequence of HCV infection ≥ 3 months prior to screening Or Subject received a cadaveric or living donor kidney at least ≥ 3 months before screening.
- 13. For subjects with a history of hepatocellular carcinoma (HCC): Subject is a recipient of a cadaveric or living donor liver transplant ≥ 3 months prior to screening as a consequence of hepatocellular carcinoma (HCC) in the setting of chronic HCV will be eligible if there is not a clinical diagnosis of recurrent HCC post-liver transplant.
- 14. Subject is currently taking a stable immunosuppressant regimen based on tacrolimus, sirolimus, everolimus, mycophenolate mofetil (MMF), azathioprine, cyclosporine and/or mycophenolic acid. Corticosteroids such as prednisone or prednisolone are permitted as components of the immunosuppressant regimen providing the dose is no more than 10 mg/day at the time of screening. Cyclosporine must be at a maintenance dose of 100 mg or less per day.

Rationale for Inclusion Criteria

1, 4-7, 9, 12, 13 In order to select the appropriate subject population with appropriate disease characteristics for evaluation

[figure not shown]

8, 14	For the safety of study subjects
2, 3	The impact of ABT-493 and ABT-530 on pregnancies is unknown
10, 11	In accordance with harmonized Good Clinical Practice (GCP)

5.2.2 **Exclusion Criteria**

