Clinical studies evaluating DDI between ABT-493 + ABT-530 and immunosuppressant drugs including tacrolimus and cyclosporine have been conducted. Results from these studies showed ABT-493 and ABT-530 did not affect cyclosporine exposure, but increased tacrolimus exposure by 50%. ABT-493 and ABT-530 exposures were not affected by tacrolimus. Cyclosporine 100 mg slightly increased exposure of ABT-493 by 37% and ABT-530 by 22%. High dose of cyclosporine (400 mg) significantly increased exposure of ABT-493 (up to 5.1-fold) and ABT-530 (up to 88%). This study will evaluate the treatment of patients in the early post-transplant period (> 3 months post liver transplant) but after the immediate post-transplant period and when its attendant complications have been addressed and CNI based immunosuppression is typically stable. As the recommended dose of cyclosporine used in this population is 75 to 150 mg BID, in order to maintain trough concentration (C_{trough}) of 75 to 125 ng/mL, no dose adjustment is needed for ABT-493 and ABT-530. A co-formulated bilayer tablet of ABT-493 and ABT-530 will be used in this Phase 3 study. Preliminary pharmacokinetic results of the Phase 3 HME bilayer tablet formulation administered under fasting conditions showed approximately 50% lower

bioavailability compared to the Phase 2 formulation at the ABT-493 300 mg + ABT-530 120 mg dose. When the Phase 3 HME bilayer tablet was administered under non-fasting conditions, exposures became relatively similar to the reference Phase 2 formulation. Hence, the Phase 3 co-formulated ABT-493 and ABT-530 HME Bilayer Tablet formulation should be administered with food (300/120 mg, $3 \times 100/40$ mg tablets) to provide DAA exposures that are similar to those of the Phase 2 formulations.

The maximum dose of ABT-493/ABT-530 will not exceed 300 mg/120 mg per day for 12 weeks.

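### The Post-Treatment Day 1 return to the pre-study dose makes no exception for cyclosporine raised on treatment for clinical need

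*Protocol*

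**What the plan says.** Protocol Section 5.2.3.2 ends with this instruction for the day after the last dose of study drug: "On Day 1 of the Post-Treatment Period, it is recommended that the pre-study dose of immunosuppressants tacrolimus, sirolimus, everolimus and cyclosporine be resumed". Section 5.1.3 has the same sentence. In both places the next sentence makes later changes depend on trough levels. Neither section conditions the Day 1 step on the reason for the on-treatment change.

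The rationale comes earlier in Section 5.2.3.2: "CNI dosing in the study is guided by the recommended dose reductions based on healthy volunteer data". For cyclosporine, however, that section recommends no reduction. It sets an entry limit, a contact rule and a ceiling of 400 mg during treatment. The contact rule, discussion with the Therapeutic Area Medical Director, applies "If the cyclosporine maintenance dose needs to be increased to a total daily dose greater than 100 mg during the Treatment Period". The entry limit is Inclusion Criterion 14: "Cyclosporine must be at a maintenance dose of 100 mg or less per day".

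The Amendment 2 rationale in Section 1.1 says the new text clarifies "cyclosporine dose adjustment during the Treatment Period for subjects requiring maintenance titration as per usual transplant standard of care".

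**The concern.** Going back to the pre-study dose makes sense when a dose was moved to offset an interaction that has now ended. That is the tacrolimus case and, by the protocol's own analogy, the sirolimus and everolimus case.

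Cyclosporine is different. Its dose limits in this trial exist because cyclosporine raises ABT-493 exposure, whereas study drug does almost nothing to cyclosporine. If cyclosporine is raised during treatment, the likely reason is that the maintenance dose was too low for the graft. That reason does not disappear when study drug stops. Amendment 2 opened the route for such increases, but the Day 1 sentence does not allow for them.

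What is at stake is under-immunosuppression of a transplant recipient for a short time, on the advice of the protocol. The efficacy analysis is not affected.

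**Working it through.** The plan gives no figure for this point, so there is nothing to reproduce. The check compares the protocol's statements and then sizes the dose change.

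**1. Is there an interaction-based reason to change the cyclosporine dose?**

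- Section 3.0, 100 mg cyclosporine: its exposures "were minimally affected by co-administration of single or steady-state doses of ABT-493 and ABT-530", with an increase of at most 14%.
- Section 3.0, 400 mg cyclosporine (preliminary results): "cyclosporine exposures were not affected by co-administration with ABT-493 and ABT-530".
- Section 5.6.4 summarises: "Results from these studies showed ABT-493 and ABT-530 did not affect cyclosporine exposure, but increased tacrolimus exposure by 50" percent.

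For tacrolimus, a 50% rise is offset by a dose cut of 1 − 1/1.5 = 33.3%, and returning to the pre-study dose correctly reverses that cut. For cyclosporine there is little or nothing to reverse. Stopping study drug lowers cyclosporine exposure by at most 1 − 1/1.14 = 12.3% (100 mg data) and by 0% on the 400 mg data.

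**2. Does the protocol foresee increases for other reasons?**

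Yes. Section 5.2.3.2 allows doses above 100 mg/day after discussion. Section 6.1.7.1 allows immunosuppressant adjustment for suspected rejection. Section 5.6.4 gives 75 to 150 mg twice daily (150 to 300 mg/day) as the recommended dose in this population, which lies above the entry cap. Up-titration is therefore plausible, although its frequency is not given.

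**3. Is there an exception anywhere?**

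None was found. Section 5.2.3.3 lets subjects revert to pre-study doses where applicable, but it concerns concomitant medication in general, 30 days after study drug.

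**4. Size of the recommended cut**

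Dose cut = 1 − (pre-study dose ÷ on-treatment dose). If a 14% study drug effect is lost as well, the fall in exposure = 1 − pre-study dose ÷ (on-treatment dose × 1.14), assuming exposure proportional to dose. The last column is an upper bound, since the 400 mg data show no effect.

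| Pre-study dose (mg/day) | On-treatment dose (mg/day) | Dose cut | Exposure fall if 14% is also lost |
|---|---|---|---|
| 100 | 125 | 20.0% | 29.8% |
| 100 | 150 | 33.3% | 41.5% |
| 100 | 200 | 50.0% | 56.1% |
| 100 | 300 | 66.7% | 70.8% |
| 100 | 400 | 75.0% | 78.1% |

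The cut is larger if the pre-study dose was below 100 mg/day. Increases that stay within 100 mg/day do not trigger the Medical Director discussion: 75 raised to 100 gives a cut of 1 − 75/100 = 25%, and 50 raised to 100 gives 1 − 50/100 = 50%.

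**5. Time before the next scheduled level**

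Appendix D defines Post-Treatment Day 1 as the day after the last study drug dose and schedules the first post-treatment level at Post-Treatment Day 3. Dosing on Days 1 and 2 therefore comes before that level.

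**The case against.** The strongest reply is that the sentence should be read with its paragraph. It follows a statement about interaction-driven reductions, so a clinician would naturally take it to reverse those and nothing else. It is also only a recommendation, and Section 5.2.3.2 makes trough levels and clinical experience the guide to dosing. An investigator who keeps a needed dose breaches nothing.

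There are also checks before the Day 1 step. Appendix C schedules a drug level and a dose modification review at Week 12/end of treatment, and levels may be taken at any time. Every scenario starting from 100 mg/day exceeds the limit that calls for Medical Director discussion. Section 5.4.1 asks for a dose modification plan for subjects discontinuing study drug, and Sections 6.1.7.1 and 6.1.8 ask for one where study drug is stopped or interrupted around rejection. Finally, the doses above are hypothetical.

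Most of this stands, and it is why the point is minor. It does not remove the conflict. The sentence names cyclosporine explicitly, and trough guidance is attached to changes made after the return, not to the return itself. The plan requirement in Section 5.4.1 sits in the text on removal of subjects and does not clearly cover those who complete 12 weeks. Increases up to 100 mg/day bypass the Medical Director. The safeguards work only if the investigator sets the written recommendation aside.

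One further objection is fair: the same gap affects tacrolimus, sirolimus or everolimus doses changed for clinical reasons, and trough-driven changes in those drugs may have mixed causes. The limit on the return should therefore apply to all four drugs.

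**Conclusion.** The concern holds, as a point to consider. For cyclosporine, the Day 1 recommendation has almost no interaction to reverse and, if followed, would undo an increase made for clinical need. The cut would be 20% to 75% for a subject who entered at 100 mg/day, against a fall of at most 12.3% attributable to stopping study drug. That fall goes in the same direction as the cut, so it gives no reason for it.

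The absence of an exception is certain from the text. The consequence is less certain. The individual doses are illustrative, the exposure figures assume proportionality to dose, and the documents give neither a cyclosporine dose distribution nor a count of affected subjects, which is probably small. The end-of-treatment review and the Post-Treatment Day 3 level limit how far and how long an error could run. SVR12, its analysis and the power are not affected.

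**What to change.** In Sections 5.1.3 and 5.2.3.2, limit the Day 1 return to doses of any of the four drugs that were changed because of the study drug interaction. Then add:

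> A cyclosporine dose changed during treatment for clinical need is continued, guided by the Week 12/EOT and Post-Treatment Day 3 trough levels.

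A cyclosporine dose lowered because of a rise attributed to study drug would still go back to its pre-study level. Where the reason for a change is mixed, mainly with tacrolimus and the mTOR inhibitors, it would help to say that the investigator decides from the end-of-treatment level.

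Under this rule the Day 1 cut for a clinically raised cyclosporine dose is 0%, leaving only the fall of at most 12.3% from stopping study drug. The cost is a small rewording in two sections. It needs no new visits, samples, data or subjects, because both levels are already scheduled.
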